Primary pharmacodynamics studies demonstrated that EPI-589 is a potent rescue agent in cellular models of diseases of energy metabolism and oxidative stress. In vitro cellular models utilizing primary human fibroblasts from patients with ALS, Parkinson's disease and other diseases characterized by high levels of oxidative stress, or striatal cells derived from mouse models of Huntingdon's disease were used to assess the potential of EPI-589 to mitigate the harmful effects of oxidative stress (Studies EPI-BA-000216, EPI-BA-000363, and EPI-BA-000362). Pretreatment of patient cells with EPI-589 potently protected against oxidative stress-mediated cell death in a concentration dependent manner. Furthermore, EPI-589 normalized 3-nitrosotyrosine (3NT) levels, a biomarker of oxidative stress, and increased glutathione levels in mouse striatal cells under oxidative stress conditions.

In secondary pharmacodynamics in vitro receptor/ion channel binding studies, EPI-589 did not significantly affect off-target molecular targets (Study EPI-BA-159). In safety pharmacology studies, EPI-589 did not significantly affect ion channel current in the hERG assay (Study 130719.FEK); did not affect ECG parameters during the 28-day and 3-month repeat-dose toxicology studies in monkey at doses up to 1,000 mg/kg/day (only Day 1 data collected for animals administered 1,000 mg/kg/day and up to Day 91 data collected for animals administered up to 300 mg/kg/day) (Studies 1660-038 and 1660-064); and did not change respiratory function or adversely impact neurobehavioral function in rat at doses up to 1,000 mg/kg (Studies 1660-051, 1660-050, and 1660-063).

In single dose exposure PK studies, EPI-589 was absorbed rapidly in rat, dog, and monkey, with mean T_{max} values ranging from .08 to 1 hour and mean $T_{1/2}$ values ranging from 3.7 to 5.0 hours (Studies EPI-BA-53, EPI-BA-59, EPI-BA-72, and EPI-BA-302). EPI-589 does not significantly induce cytochrome P450 (CYP) enzymes and appears to be metabolized by reductases in the

liver cytosol and microsomal subcellular fractions and to a lesser extent by the family of CYP enzymes (Studies MC12M-0037 and MC14M-0018).

EPI-589 exhibited weak direct inhibition of CYP2B6, CYP2C8, CYP2C9, and CYP3A4/5 (both midazolam and testosterone as probe substrates) with estimated IC_{50} (μM) values and R values based on free plasma concentrations (shown in parentheses) of 28 (1.25), 40 (1.18), 92 (1.08), 34 (1.21), and 53 (1.13), respectively (Study MC14M-0020) Based on these data, EPI-589 is not anticipated to increase the risk of adverse developmental or reproductive outcomes in humans when used in accordance with dosing information.

D2. Clinical Studies

Phase I Study EPI589-13-022 evaluated the pharmacokinetics, safety and tolerability of single ascending oral doses (SADs) of EPI-589 in healthy subjects and a preliminary evaluation of safety and tolerability data was performed. Sixteen AEs were reported in the 36 subjects who received administration of EPI-589. Ten subjects (27.8%) who received EPI-589 (and 2 subjects, 20% on placebo) reported AEs that were assessed as related. All were mild and resolved during the study, with the exception of a common cold (1 subject) and cold sore (1 subject). None of the vital signs, ECG parameters or clinical laboratory test results showed a clinically relevant change compared to baseline. From all preliminary data available from this SAD study it may be concluded that there is no objection to proceed with treatment with 50 mg, 100 mg, 250 mg or 500 mg of EPI-589.

Phase I Study EPI589-14-01 evaluated the pharmacokinetics, safety and tolerability of multiple ascending oral doses (MAD) of EPI-589 in healthy subjects, and an evaluation of safety and tolerability data was performed. No severe or serious adverse events were observed. Twenty-six subjects (65.0%) on EPI-589, and 8 subjects (80%) on placebo reported AEs. Twenty-four of 34 AEs were considered by the Investigator to be related to EPI-589. Nineteen subjects (47.5%) on EPI-589, and 6 subjects (60%) on placebo reported AEs that were assessed as related. All adverse events were mild, except for 1 AE which was moderate (unrelated brain contusion). All AEs were resolved during the study, with the exception of one, which was a common cold. None of the vital signs, ECG parameters or clinical laboratory test results showed a clinically relevant change compared to baseline. From all preliminary data available from the MAD study it may be concluded that there is no objection to proceed with treatment with 250-mg, or 500-mg doses of EPI-589.

E. Human Pharmacokinetics

EPI-589 was fast absorbed following oral administration in SAD Study EPI589-13-022. The median C_{max} was attained approximately within 1 hour under fasted conditions after dosing. The median T_{max} values were attained in 0.50 to 1.00 hours over the dose range of 50 to 1000 mg under fasted conditions and 3.01 hours at the 500 mg dose level under fed conditions. Mean half-life ranged from 5.55 to 10.7 hours over the dose range of 50 to 1000 mg under fasted conditions and 4.91 hours at the 500 mg dose level under fed conditions. Half-life was independent of the dose levels over the dose range of 50 to 1000 mg under fasted conditions. The rate of EPI-589 absorption, as measured by C_{max} , was decreased by 24.07% under fed conditions at the 500 mg

dose level. The extent of absorption as measured by AUCs (AUC_{0-t} or AUC_{0-inf}) was not affected under fed conditions in the 500 mg dose groups.

In MAD study EPI589-14-01, EPI-589 was rapidly absorbed following oral administration and the median C_{max} was attained within 1 hour (0.50 to 0.76 hours) under fasted conditions after single or multiple dosing among these five cohorts. The mean half-life of EPI-589 ranged from 5.64 to 8.47 hours among these five cohorts. In general, the mean values of the time to peak concentration (T_{max}), half-life (t_{1/2}), apparent terminal constant (λz), accumulation ratio (AR), percent fluctuation (%F) and accumulation index (AI) of EPI-589 were similar among the five cohorts of various ages and smoking status. No significant effects of age or smoking on EPI-589 pharmacokinetics were observed in this study. Dose proportionality existed in the exposures (AUC_{0-tau}, C_{max}, C_{min} and C_{avg}) over the dose range of 250 to 500-mg BID EPI-589 under fasted conditions.

F. Clinical Study

EPI589-15-002: A Phase 2A Safety and Biomarker Study of EPI-589 in in Mitochondrial Subtype and Idiopathic Parkinson's Disease Subjects.

G. Selection of Drugs and Dosages

The study drug in this trial is EPI-589: common chemical name (R)-troloxamide quinone.

Each tablet contains 250 mg of EPI-589. The study dose is 500-mg BID, to be maintained in the absence of treatment-emergent toxicity. EPI-589 tablets must be taken with meals.

H. Compliance Statement

This study will be conducted in full accordance with all applicable research policies and procedures, the EU Clinical Trials Directive, all applicable EU and US federal and local laws and regulations including 45 CFR 46, 21 CFR Parts 50, 54, 56, 312 and 314, and the Good Clinical Practice: Consolidated Guideline approved by the International Conference on Harmonization (ICH). Any episode of noncompliance will be documented.

The investigators will perform the study in accordance with this protocol, will obtain consent and will report AEs in accordance with local institutional policies and procedures and all EU and US federal requirements. Collection, recording, and reporting of data will be accurate and will ensure the privacy, health, and welfare of research subjects during and after the study.

I. Relevant Literature and Data

Literature references have been provided in Section [XIV](#). Additional information can be found in the Investigator's Brochure.

III. STUDY OBJECTIVES

A. Primary Objective

The primary objective of this study is to evaluate the effects of EPI-589 safety as assessed by occurrence of drug-related serious adverse events in subjects with PD.

B. Secondary Objectives

The secondary objectives are to evaluate the effects of EPI-589 in subjects with PD on:

1. Glutathione cycle biomarkers as measured in blood, cerebral spinal fluid, and urine
2. Clinical disease state as assessed by the Movement Disorder Society-sponsored revision of the Unified Parkinson's Disease Rating Scale (MDS-UPDRS)
3. Disease morbidity as assessed by the Non-motor Symptoms Scale (NMSS), PDQ-39 and EQ-5D
4. Cognitive function as assessed by Montreal Cognitive Assessment (MoCA)
5. Mood as assessed by the Beck Depression Inventory (BDI) and the Montgomery & Asberg Depression rating scale (MADRS)
6. Pharmacokinetics
7. Hematology, blood chemistry, electrocardiogram

Space intentionally left blank

IV. INVESTIGATIONAL PLAN

A. General Schema of Study Design

Following study enrollment, baseline assessments will be performed. Subjects will participate in a 30-day run-in phase to establish biomarker and clinical baseline measurements. EPI-589 will then be administered for up to 3 months unless discontinued for safety or tolerability issues.

Under an adaptive design strategy, additional subjects (up to 20) may be added to increase the number of biomarker responsive idiopathic PD subjects.

A1. Screening Phase

Suitable candidates for the trial will receive a short overview of the study by the Investigator's staff and, if interested, will undergo Screening. The Investigator will inform each prospective subject of the nature and details of the study, explain the potential risks and must obtain written informed consent from the subject or their legally authorized representative prior to performing any study related procedures.

A2. 30-Day Run-in Phase

Once eligibility is confirmed, the subject will be enrolled in the study and the run-in scans, CNS, blood-based biomarker, urine-based biomarker and clinical measurements will be collected.

A3. Baseline

Baseline assessments, scans, blood-based biomarker, urine biomarker, and clinical measurements will be collected.

A4. Treatment Phase

EPI-589 dosing will start on Day 1. Subjects will self-administer EPI-589 at a dose of 500-mg BID.

Blood-based biomarker, urine biomarker, and clinical measurements will be collected at Day 29 (\pm 3 days) and Day 85 (\pm 3 days).

A5. End of Study

End of study data will be collected at the last study visit Day 85 (\pm 3 days).

AEs reported as ongoing at Day 85, any associated concomitant medications associated with such events, and any events occurring within 30 days of last dose will be followed for 30 days.

B. Randomization and Blinding

This is an open-label study.

C. Study Duration, Enrollment and Number of Sites

C1. Duration of Subject Treatment

Subjects will participate in a 30 day run-in phase to establish biomarker and clinical baseline measurements. EPI-589 will then be administered for 3 months unless discontinued for safety or tolerability issues.

C2. Total Number of Study Sites/Total Number of Subjects Projected

This study will be conducted at two study sites:

- [REDACTED] UK
- [REDACTED] USA.

Approximately 40 subjects with PD are projected:

- 20 with genetically-defined subtypes
- 20 PD drug-naïve

Under an adaptive design strategy, additional subjects (up to 20) may be added to increase the number of biomarker responsive idiopathic PD subjects.

D. Study Population

D1. Inclusion Criteria

1. Hoehn and Yahr stage \leq 2.5
2. Ambulatory with or without assistance
3. Agreement to use contraception if within reproductive years
4. Willingness and ability to comply with study procedures
5. Stable regimen of dietary supplements for 30 days prior to enrollment
6. Abstention from use of other investigative or non-approved drugs for the duration of the trial

For Idiopathic Subjects

7. *For idiopathic subjects:* a diagnosis of early idiopathic PD confirmed by the presence of bradykinesia plus one or both of the following symptoms: rigidity or resting tremor; and with an abnormal DaTscan consistent with a dopaminergic deficit
8. *For idiopathic subjects:* must not yet require symptomatic medications for PD and not expected to require such treatment before the end of the study
9. *For idiopathic subjects:* age 40 to 75 years
10. *For idiopathic subjects:* within 5 years of diagnosis of Parkinson's disease

For Genetic Subtype Subjects

11. *For genetic subtype subjects:* a confirmed diagnosis of PD plus a genetic diagnosis consistent with PD, specifically PINK1, parkin, LARK2 or other mitochondrial genetic subtype
12. *For genetic subtype subjects:* age 21 to 75 years
13. *For genetic subtype subjects:* stable medication regimen of PD drugs for 30 days (except 60 days for rasagiline) prior to enrollment

D2. Exclusion Criteria

1. Allergy to EPI-589 or other components of the EPI-589 tablet formulation
2. Use of antioxidant supplements, specifically vitamins E and C beyond the recommended daily allowance
3. Other Parkinsonian disorders
4. MoCA score of <24
5. Revised Hamilton Rating Scale for Depression ≥ 11
6. Parkinsonism due to drugs or toxins
7. Diagnosis of any other clinically significant neurologic disease that will confound the assessment of effect of study drug on disease progression
8. Malignancy within past two years
9. Pregnant or plans to become pregnant or breast feeding
10. History of stroke
11. History of brain surgery
12. Hepatic insufficiency with liver function tests (LFTs) > 3 times upper limit of normal
13. Renal insufficiency as defined by creatinine > 1.5 times normal
14. End stage cardiac failure
15. Participation within past 3 months and for duration of study in a trial of a device, drug or other therapy for PD

For Idiopathic Subjects

16. *For idiopathic subjects:* use of any MAO inhibitors, amantadine or other drugs prescribed for core symptoms of Parkinson's disease for idiopathic subjects
17. *For idiopathic subjects:* use of nortriptyline or fluvoxamine 60 days prior to enrollment

Space intentionally left blank

V. STUDY PROCEDURES

A. Screening Visit

Screening evaluations will be performed within two months of first dose. The Investigator will inform each prospective subject of the nature of the study, explain the potential risks, and must obtain written informed consent from the subject prior to performing any study-related procedures and prior to the administration of study drug. Screening evaluations consist of the following:

1. Assessment of eligibility
2. Medical history, chart review
3. Receipt and review of previous testing including genetic tests
4. Physical examination including vital signs
5. Height and weight
6. 12-lead ECG
7. Laboratory assessments for hematology, coagulation, and serum chemistry (See Sections [VI.D3.a](#) and [VI.D3.b](#))
8. Urine pregnancy test (women of childbearing potential must have a negative urine pregnancy test; see Section [VI.D3.c](#))
9. MoCA
10. DaTscan
11. Revised Hamilton Rating Scale for Depression
12. Concomitant medications assessment (last 60 days prior to enrollment)

A1. Run-in Assessments

If the subject is eligible for the study following all screening procedures and is still willing to participate in the study, the subject must return to the clinic within one month for Run-in assessments. These will be performed 30 days (\pm 3 days) prior to baseline after eligibility is confirmed and subject is enrolled in the study. Run-in evaluations consist of the following:

1. Blood-based glutathione cycle biomarkers
2. CNS biomarkers (lumbar puncture)
3. Urine biomarkers

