Post-Treatment Follow-up will be at least 10 days after last dose and if there are any ongoing or new AEs noted at month 3, then the follow up will be up to 30 days after last dose. AE/SAE and concomitant medication assessments conducted by telephone. Additional assessments to be determined at Investigator discretion.

B. Randomization and Blinding

This is an open-label study.

C. Study Duration, Enrollment and Number of Sites

C1. Duration of Subject Treatment

Subjects will participate in a 30-day run-in phase to establish biomarker and clinical baseline measurements. EPI-589 will then be administered for 3 months (85 days \pm 3 days) unless discontinued for safety or tolerability issues. A post-treatment follow-up will be conducted at least 10 days and up to 30 days after last dose.

C2. Total Number of Study Sites/Total Number of Subjects Projected

This study will be conducted at five study sites:

- [REDACTED] UK
- [REDACTED] USA.
- [REDACTED] Germany
- [REDACTED] USA
- [REDACTED] USA

Approximately 40 subjects with PD are projected:

- 20 with genetically-defined subtypes
- 20 PD idiopathic PD

Under an adaptive design strategy, additional subjects (up to 20) may be added to increase the number of biomarker responsive idiopathic PD subjects to achieve a higher number of subjects in

whom we could understand the biochemical effects of the investigative drug and its potential clinical impact as assessed by the same study protocol and outcome metrics.

D. Study Population

D1. Inclusion Criteria

1. Hoehn and Yahr stage ≤ 3.0
2. Ambulatory with or without assistance
3. Sexually active fertile subjects and their partners must agree to use medically accepted methods of contraception (e.g., hormonal methods, including oral, subcutaneous, and intrauterine; barrier methods, including [REDACTED] condom, [REDACTED] condom, or diaphragm with spermicidal gel) during the course of the study and for 3 months after the last dose of study treatment.
4. Willingness and ability to comply with study procedures
5. If on medications for PD drugs, then medication regimen must be stable for 60 days prior to enrollment
6. Abstention from use of other investigative or non-approved drugs for the duration of the trial

For Idiopathic Subjects

7. A diagnosis of idiopathic PD confirmed by the presence of bradykinesia plus one or both of the following symptoms: rigidity or resting tremor; and with an abnormal DaTscan consistent with a dopaminergic deficit

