9. MDS-UPDRS
10. MoCA
11. DaTscan (for idiopathic subjects only)
12. Revised Hamilton Rating Scale for Depression
13. SAE assessments
14. Concomitant medications assessment (last 60 days prior to enrollment)

*Breast exam is at screening physical exam only.

** Height is measured at screening visit only.

***Screening values can be used if done within one month of baseline and if completed under fasted conditions

A1. Run-in Assessments

If the subject is eligible for the study following all screening procedures and is still willing to participate in the study, the subject must return to the clinic within one month for Run-in assessments. These will be performed 30 days (\pm 3 days) prior to baseline after eligibility is confirmed and subject is enrolled in the study. Run-in evaluations consist of the following:

1. Fasting blood-based glutathione cycle biomarkers
2. Fasting CNS biomarkers (lumbar puncture)
3. Fasting urine biomarkers
4. Timed motor tests (for subjects on dopamine therapy)
5. AE/SAE assessments
6. Concomitant medications review

B. Treatment Phase

After the Run-in phase, the subject must return to the clinic within 30 days (± 3 days) for baseline assessments. In-clinic study visits are scheduled at Month 1 and Month 3. The Month 2 study assessments can be conducted via telephone. End of treatment assessments will be conducted at the Month 3 study visit. Pharmacokinetic sampling takes place at Month 1 and Month 3. The baseline and all subsequent laboratory assessments should be obtained under fasting conditions.

B1. Baseline Assessments

The following will be assessed or performed at this visit.

1. Physical examination including vital signs
2. Height and weight*
3. 12-Lead ECG*
4. Fasting blood-based GSH cycle biomarkers
5. Fasting urine-based biomarkers
6. Laboratory assessments for hematology, coagulation and serum chemistry*
7. Urine pregnancy test (females of child bearing potential)
8. C-SSRS (Columbia Suicide Severity Rating Scale)

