6. C-SSRS
7. Fasting blood-based GSH cycle biomarkers
8. Fasting urine-based biomarkers
9. Fasting CNS biomarkers

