The following are prohibited while the subject is on study treatment:

1. Use of antioxidants, specifically vitamins E and C beyond the recommended daily allowance. However if the subjects are on high doses of Vitamin E and C and are eligible to participate, they are allowed a 2 weeks washout period prior to enrollment
2. Participation 3 months prior to and for the duration of the study in a trial of a device, drug or other therapy for PD

H. Subject Withdrawals

Subjects receive study treatment until treatment discontinuation for one of the reasons listed below. However, subjects may discontinue study treatment or withdraw their consent to participate in the study at any time without prejudice. The following conditions require subject discontinuation from all study treatment:

1. At their own request or at the request of their legally authorized representative
2. If a subject experiences an adverse event that is deemed related to treatment with EPI-589 and in the Investigator's or the Sponsor's medical judgment continuation of treatment would be detrimental to the subject.
3. At the specific request of a regulatory agency for termination of treatment of an individual subject or all subjects under the protocol
4. Subject participation in another clinical study using an investigational agent or investigational medical device
5. Use of prohibited medications such as vitamins E and C beyond the recommended daily allowance.
6. Refusal of sexually active fertile subjects (excluding subjects who have been sterilized) to use medically accepted methods of contraception
7. If a subject becomes pregnant.
8. Significant noncompliance with the protocol in the opinion of the Investigator or the Sponsor

In all cases, the reason for withdrawal must be recorded in the CRF and in the subject's medical records. If the reason is not known, the subject must be followed to establish whether the reason was due to an AE, and, if so, this must be reported in accordance with the procedures in Section [X.B.](#)

Evaluations should be performed on all subjects who participate but do not complete the study according to protocol. Dropouts may be replaced at the request of the Sponsor. The Investigator will make every effort to contact subjects lost to follow-up.

Every effort will be made to follow subjects who have an ongoing AE at the time of withdrawal until the event resolves, or until the Sponsor and the Investigator agree that further follow-up is not medically necessary.

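### The three-month look-back on earlier trials covers only PD therapies, so the single pre-treatment CSF sample has no required interval after a non-PD investigational drug

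*Protocol*

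**What the plan says.** The current protocol states its rule on other trials in several places, with two different scopes.

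- **Before and during the study, limited to PD.** Exclusion 15 in V.D2, repeated in the synopsis: "Participation within past 3 months and for duration of study in a trial of a device, drug or other therapy for PD". VI.G (Prohibited Medications), item 2: "Participation 3 months prior to and for the duration of the study in a trial of a device, drug or other therapy for PD".
- **During the study, any agent.** Inclusion 6 in V.D1 requires "Abstention from use of other investigative or non-approved drugs for the duration of the trial". VI.H (Subject Withdrawals), item 4, lists among the conditions for discontinuation "Subject participation in another clinical study using an investigational agent or investigational medical device".

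On sampling, VI.A1 says that after screening "the subject must return to the clinic within one month for Run-in assessments", and that these assessments fall 30 days (± 3) "prior to baseline after eligibility is confirmed and subject is enrolled in the study". Lumbar puncture is in the Run-in list and, as "Fasting CNS biomarkers", in the Month 3 list. It is in neither the Baseline nor the Month 1 list. Blood and urine glutathione markers are collected at Run-in, Baseline, Month 1 and Month 3. Section VIII.A plans changes from baseline to Month 3 for peripheral and CNS biomarkers within each subject. The synopsis names no reference therapy.

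**The concern.** The look-back depends on the indication of the earlier trial, whereas the on-study rules depend on whether the agent is investigational. For a biomarker study the second basis is the relevant one, because an unapproved drug can affect redox markers whatever disease it was being tested for. A study in the protocol's own reference list reports, by its title, an agent that raised brain and blood glutathione in Gaucher as well as Parkinson disease.

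The protocol already guards against this kind of interference elsewhere. It provides a 2-week washout for high-dose vitamins E and C (VI.G item 1) and requires 60 days of stable PD medication (inclusion 5). It sets no interval for an investigational drug from a non-PD trial.

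What is at stake is the CSF change. If the Run-in value is shifted by a residual effect that has gone by Month 3, the shift appears in full, with the opposite sign, as a change on EPI-589. There is no second pre-treatment CSF sample and no control arm with which to detect or remove it.

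**Working it through.** The plan gives no figure of its own on this point, so the check compares the texts and then bounds the intervals they enforce.

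**1. Is there any other look-back?** The rules that reach back before enrolment are:

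| Rule | Reach | Covers a non-PD investigational drug? |
|---|---|---|
| Exclusion 15 and VI.G item 2 | 3 months | No, on the natural reading |
| Inclusion 5 | 60 days | No, PD medication only |
| VI.G item 1 | 2 weeks | No, vitamins E and C only |
| VI.F Concomitant Medication | 60 days | Recorded, not barred |
| Inclusion 6 | none, runs forward | Barred once the trial has begun |

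No rule sets an interval since the last dose of a non-PD investigational drug.

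**2. Enforced interval to the Run-in CSF sample.**

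- PD agent: at least 3 months.
- Non-PD agent: Run-in must fall within one month of screening, and no minimum is stated. If abstention under inclusion 6 starts at enrolment, the enforced interval is 0 days. If it starts at screening, the interval equals the screening-to-Run-in gap, 0 to about 30 days.

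**3. Which matrices are exposed?** Baseline follows Run-in by 30 ± 3 = 27 to 33 days, and inclusion 6 applies throughout that time. Blood and urine therefore have a second pre-treatment sample at least 27 days after any other investigational dose. CSF does not. Its two samples are separated by (27 to 33) + (82 to 88) = 109 to 121 days.

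**4. Effect on the estimate.** Let c be the residual effect of the earlier agent on the Run-in CSF value, gone by Month 3. Then

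observed change = Month 3 value − (true pre-treatment value + c) = true change − c.

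The documents give no basis for a value of c.

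**5. Illustration of why the interval matters.** The fraction of drug remaining is 2^(−gap/half-life). The half-lives are assumptions and are not in the documents.

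| Assumed half-life | 0 days | 7 days | 30 days | 90 days |
|---|---|---|---|---|
| 1 day | 100% | 0.8% | about 0% | about 0% |
| 7 days | 100% | 50% | 5.1% | 0.01% |
| 21 days | 100% | 79% | 37% | 5.1% |

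For short half-lives the gap matters only if Run-in follows the last dose within days. For long half-lives it matters across the whole permitted range. Residual drug is only a rough guide to residual effect on glutathione, which could be shorter or longer.

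**The case against.** The best defence is that a narrow rule before the study and a broad rule during it is a common structure, and that neither passage misstates the other. That has some force. However, VI.G item 2 and VI.H item 4 both govern participation during the study and still differ in scope, so there is something to reconcile.

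The sentence could also be parsed so that the PD limit attaches only to the last item, other therapy. The look-back would then cover any drug or device trial. This is not the natural reading, and if sites can read it both ways the wording still needs repair.

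In practice screening takes time: it includes laboratory tests, cognitive and mood scales and, for idiopathic subjects, a DaTscan. A gap of 0 days is a bound and not an expected value. The other exclusions (malignancy, stroke, organ insufficiency, confounding neurologic disease) also remove some people likely to come from non-PD trials. Both observations stand, and they reduce the likely frequency.

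A reader might infer two stronger points. The first is that the primary endpoint is at risk, because a late serious event from the earlier drug could be counted as related to EPI-589. X.C4 does allow an event that other therapy could have caused to be graded possibly related. But the Run-in period puts about 27 to 33 days before dosing, the earlier drug is recorded if taken within 60 days of enrolment, and the investigator weighs other therapy when grading. That route is remote and the documents do not show it. The second is that all the glutathione markers are compromised. They are not, because blood and urine are sampled again at Baseline and the planned change runs from baseline. Nor is one subject's share of a group mean a measure of bias.

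**Conclusion.** The point holds for the CSF biomarker and goes no further. The current text admits a subject from a non-PD investigational drug trial with no required interval before the only pre-treatment lumbar puncture, while it requires 3 months after a PD trial. Any carry-over in that sample would pass straight into the within-subject change and could not be removed afterwards.

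The size cannot be stated, because the documents give no frequency of such subjects, no half-life and no effect on glutathione. The conclusion rests on the natural reading of the PD limit and on the assumption that affected subjects would be few. CSF is one secondary measure, and no formal statistical comparison is planned for the analysis populations. This is a worthwhile tidy-up and not a threat to the study's conclusions.

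**What to change.** Reconcile the scope of exclusion 15 (synopsis and V.D2) and VI.G item 2 with inclusion 6 and VI.H item 4, so that the existing look-back applies to trials of any investigational drug or device and not only those for PD. That is one change of wording in three places, and it also removes the grammatical ambiguity. It belongs in the protocol, because no analysis plan can restore a clean CSF baseline.

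The cost is that a few candidates wait up to 3 months or are excluded. The change has two limits. It does not address approved drugs stopped shortly before enrolment, and the 3-month period is carried over from the existing rule and not derived for non-PD agents.

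For subjects already enrolled, the 60-day medication record can identify most of those concerned, though not anyone whose last dose was between 60 days and 3 months earlier. The CSF change can then be shown with and without them.
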